### **3.3.3 Secondary Efficacy Endpoints**

The secondary endpoints will include the time to diagnosis of CDMS, severity of disease evaluated by EDSS, SDMT and MSFC, and brain MRI results. Number and percentage of subjects with diagnosis of CDMS will be summarized, and descriptive statistics of time to diagnosis of CDMS will be presented. EDSS, SDMT, MSFC, and brain MRI outcomes will also be summarized using descriptive statistics.

### **Clinically definite multiple sclerosis (CDMS) and time to diagnosis of CDMS**

The number and percentage of subjects with diagnosis of CDMS will be displayed by treatment groups. The time to diagnosis of CDMS will be summarized using descriptive statistics .

Time to confirmed MS is the time from the diagnosis of Acute optic neuritis (AON) to the confirmed MS date.

Subjects who do not have a confirmed MS will be considered censored. The censor date for subjects is the time of the last study contact. The start date for calculation of day to censor is the date of diagnosis of AON in 215ON201.

The proportion of subjects with a confirmed MS from the diagnosis of AON in 215ON201 to Day 1 in 215ON203, and the time to diagnosis of CDMS in 215ON203 from the diagnosis of AON in 215ON201 will be analyzed by the Kaplan-Meier (KM) product limit estimate. The KM estimate for the proportion of patients with MS and 10th percentile, 25th percentile and 50th percentiles of time to MS will be summarized by treatment group.

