#### Analysis population

Intent-to-treat (ITT) population, per-protocol population, and safety population are defined as follows.

- *Intent-to-Treat Population*

The intent-to-treat population is defined as all randomized subjects who received at least 1 dose of study treatment (BIIB033 or placebo) in 215ON201 study, and completed at least one of the 1-day assessments in this study.

- *Per-protocol Population*

The per-protocol population is defined as subjects from the ITT population who completed the 215ON201 study, did not miss more than one dose of BIIB033 or placebo, and did not receive MS modifying therapies during study 215ON201. These subjects were included in the per-protocol population of 215ON201 study.

- *Safety population*

The safety population is defined as all subjects who received at least 1 dose of study treatment in 215ON201 and completed at least one of the 1-day assessments in this study.

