## **3.3 Efficacy Analysis**

### **3.3.1 General consideration for efficacy analysis**

#### Analysis population

All efficacy endpoints will be evaluated in the ITT and per-protocol population as defined in Section 3.1.

The analyses performed in the per-protocol population will be considered the primary analyses, and the analyses based on ITT population will be considered as sensitivity analyses.

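### The CDMS Kaplan-Meier analysis starts at AON diagnosis but admits only subjects who returned 2 or more years later, so dosed non-returners are excluded where they could be censored

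*SAP*

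**What the plan says.** SAP 3.3.3 sets the origin: "Time to confirmed MS is the time from the diagnosis of Acute optic neuritis (AON) to the confirmed MS date". For subjects without confirmed MS it adds "The censor date for subjects is the time of the last study contact" and "The start date for calculation of day to censor is the date of diagnosis of AON in 215ON201". The proportion with MS and the time to CDMS "will be analyzed by the Kaplan-Meier (KM) product limit estimate", with the 10th, 25th and 50th percentiles by treatment group. No between-arm test is named for CDMS.

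The population is fixed elsewhere. SAP 3.3.1 states: "All efficacy endpoints will be evaluated in the ITT and per-protocol population as defined in Section 3.1". Under SAP 3.1 the ITT set requires dosing in 215ON201 and that the subject "completed at least one of the 1-day assessments in this study". The per-protocol set is a subset of it, and SAP 3.3.1 puts that subset first: "The analyses performed in the per-protocol population will be considered the primary analyses". Protocol 14.1.1 likewise bases efficacy on enrolled subjects who complete the Day 1 assessments. The visit falls no earlier than 2 years after Week 32, or projected Week 32 (protocol 7.2.1).

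**The concern.** The clock starts years before the event that decides who is analysed. Kaplan-Meier can use a subject followed for part of the period, and the SAP's censoring rule would suit a dosed subject last seen in 215ON201. The population definition prevents the rule from reaching that subject. A non-returner who converted during the parent study is lost as an event, and one who did not is lost as person-time.

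Incidence of CDMS and time to CDMS are the first-listed secondary endpoints (protocol 6.2, SAP 1.2). If conversion changes the chance of coming back, the displayed incidence and percentiles describe a selected group. If that dependence differs by arm, the contrast between the curves is affected too.

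**Working it through.** **Who is analysed.** Both efficacy sets require a 215ON203 assessment. Nobody analysed is therefore censored before the earliest return visit, and up to that time the Kaplan-Meier estimate equals the crude proportion among returners.

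**Inputs from the documents.** Dosed subjects: 41 + 41 = 82 (protocol 5.5.2), which reproduces the stated maximum. Parent follow-up runs to Week 32, 32/52.18 = 0.613 years; the earliest return is 2.613 years. The small gap between AON diagnosis and first dose is ignored.

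**Assumptions.** The documents give no CDMS rate or return rate. I use CDMS of 30% by 2.613 years (range 20-50%), a constant hazard, return of 60-90%, and non-returners followed to Week 32 with MS status known. At 30%, the hazard is -ln(0.70)/2.613 = 0.1365 per year, so Week 32 incidence is p1 = 1 - exp(-0.1365 × 0.613) = 0.0803.

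**Precision, if return is unrelated to CDMS (no bias either way).** Per arm, n = 41, return r.
- Week 32: returners √[p1(1-p1)/(41r)], all dosed √[p1(1-p1)/41]. The SE falls by 1 - √r, from 5% (r = 0.9) to 23% (r = 0.6). At r = 0.7 it goes from 0.051 to 0.042.
- 2.6 years, r = 0.7: returners √[0.30 × 0.70/28.7] = 0.0855. All dosed by Greenwood, with q = (0.30 - 0.0803)/0.9197 = 0.2389: 0.70 × √[0.0803/(0.9197 × 41) + 0.2389/(0.7611 × 41 × 0.9197 × 0.7)] = 0.0829, a 3% gain. Over the whole assumed range the gain is 1-4%.

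**Bias, if return depends on CDMS status by the visit.**
- Return 90% with CDMS, 60% without. Returners only: 0.27/(0.27 + 0.42) = 39.1%. All dosed: 1 - 0.9197 × 0.42/(0.42 + 0.2197 × 0.90) = 37.5%.
- Return 60% with CDMS, 90% without. Returners only: 0.18/(0.18 + 0.63) = 22.2%. All dosed: 1 - 0.9197 × 0.63/(0.63 + 0.2197 × 0.60) = 23.9%.
- Week 32, returners only: 0.0803 × 0.90/0.69 = 10.5%, or 0.0803 × 0.60/0.81 = 5.9%.

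The 10th percentile is found by solving the same expressions for a cumulative incidence of 0.10.

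| Quantity | True | Returners only | All dosed |
|---|---|---|---|
| CDMS at Week 32 | 8.0% | 10.5% or 5.9% | 8.0% |
| 10th percentile of time to MS | 40 weeks | 30 or 55 weeks | 38 or 43 weeks |
| CDMS at 2.6 years | 30% | 39.1% or 22.2% | 37.5% or 23.9% |

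A simulation (3,000 runs, 41 per arm) gave means at 2.6 years, returners only against all dosed, of 0.390 against 0.373 and 0.223 against 0.240; with equal 70% return, 0.303 against 0.302.

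**Bias, if return depends only on conversion by Week 32.** Returners only: (0.0803 × 0.90 + 0.2197 × 0.60)/(0.0803 × 0.90 + 0.9197 × 0.60) = 32.7%, or 28.1% with the rates reversed. All dosed restores 30.0%.

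**A second set of assumptions.** Take 15% CDMS by Week 32 and 30% two years later, 80% return among all converters and 60% overall. Returners only: 0.24/0.60 = 40.0%. All dosed: 1 - 0.85 × 0.36/(0.36 + 0.12) = 36.3%. Again most of the late bias stays.

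**The case against.** The strongest reply is that the documents show no bias. They give no return rate and no link between return and CDMS, and without such a link the bias is zero. A reader might infer that the curves are certainly biased, or that this is immortal time. Neither follows: CDMS does not prevent return, so selection is possible but not built in. A reader might also infer a false arm difference. That needs return, or its dependence on CDMS, to differ by arm, and protocol 9.3 keeps sites and patients blind to parent treatment. These limits stand.

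A second reply concerns data. Complete parent follow-up of every dosed subject cannot be assumed, because the plan provides for a projected Week 32 when visits were missed; the Week 32 gains above are therefore upper bounds. Nor do the documents say that CDMS was ascertained in 215ON201. Protocol 11.1 takes the CDMS date from history at the follow-up visit, and Table 1 starts that history after the last parent visit. This stands as a condition on the fix. But SAP 3.3.3 already covers MS from AON diagnosis to Day 1, so unless the Day 1 MS diagnosis item reaches back, the planned analysis needs parent-period dates for returners as well.

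Third, protocol 14.1.1 defines a returner population, the endpoint is summarised descriptively and there is no power basis. That argues for adding an analysis and against replacing the planned one. It gives no reason to leave usable follow-up out altogether.

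**Conclusion.** The mismatch between time origin and population is on the page, and nothing in either document adds non-returners back. Its effect is conditional. Under the assumed rates, selection on return moves Week 32 incidence by about 2 points on a true 8.0% and the 10th percentile by about 10 to 15 weeks; an all-dosed analysis removes the first and most of the second. At 2.6 years the possible bias is 8 to 9 points, of which the all-dosed analysis removes only 1.6 to 1.7 if later converters also return selectively. A reader might infer that censoring at parent contact cures the 2-year estimate; it does so only if return depends on nothing later than parent-period conversion. The precision gain matters at Week 32 and is slight at 2.6 years. This is a cheap improvement to a descriptive secondary endpoint and leaves the protocol's own set in place.

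**What to change.** Keep the protocol-defined set and add to SAP 3.3.3:

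> CDMS incidence and time to CDMS will also be estimated by Kaplan-Meier in all 82 subjects randomised and dosed in 215ON201, by original arm. Subjects not assessed in 215ON203 contribute any confirmed MS event recorded in 215ON201 under the same definition, and are otherwise censored at their last 215ON201 contact at which MS status was known. Numbers at risk will be shown at Week 32 and at 2 years after Week 32. Return to 215ON203 will be tabulated by arm and by parent-study MS status.

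The cost is one SAP paragraph and a pull of MS-status and last-contact dates from the parent database. The SAP should state three downsides:
- The analysis is possible only if the parent database holds usable MS-status dates.
- Ascertainment may differ, with retrospective history for returners and parent records for non-returners.
- Only selection on parent-period conversion is corrected, so informative non-return after Week 32 leaves most of the later bias.

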4.2. Schedule of Activities

Table 1: Schedule of Activities

Tests and Assessments ¹	Day 1 ² : (2 Years + up to 12 Months After Week 32 Visit in Study 215ON201 or Projected Week 32 Visit if the Subject Did Not Complete All Visits)
Informed Consent	X
Eligibility Criteria Check	X
Medical History ³	X
Multiple Sclerosis Diagnosis	X
Multiple Sclerosis Signs and Symptoms	X
Concomitant Therapy and Procedures Recording	X
Vital Signs ⁴	X
Physical Examination	X
Expanded Disability Status Scale ⁵	X
Symbol-Digit Modalities Test	X
Multiple Sclerosis Functional Composite Including 
 • Timed 25-Foot Walk • 9-Hole Peg Test (Dominant and Nondominant Hands) • (3-Second) Paced Auditory Serial Addition Test 	X

CONFIDENTIAL

The information contained herein may not be used, disclosed, or published without the written consent of Biogen MA Inc.

Tests and Assessments ¹	Day 1 ² : (2 Years + up to 12 Months After Week 32 Visit in Study 215ON201 or Projected Week 32 Visit if the Subject Did Not Complete All Visits)
[REDACTED]	[REDACTED]
Full-Field Visual Evoked Potential ⁷	X
[REDACTED]	[REDACTED]
Adverse Event/Serious Adverse Event Recording ¹²	X

[REDACTED] MRI = magnetic resonance imaging.

¹ All assessments should be performed on the same day and in the order listed, when possible (or within a +5-day window of the 1-day visit).

² Completion of the Day 1 visit assessments constitutes the end-of-study visit.

³ Medical history will be taken from after last study visit in Study 215ON201.

⁴ Vital signs include temperature, systolic and diastolic blood pressure, pulse rate, body weight, and respiratory rate (after sitting for at least 5 minutes).

⁵ Expanded Disability Status Scale should be performed by a study certified rater. Where applicable, refer to study manual for instructions.

⁶ [REDACTED]

⁷ Sites and technicians must be qualified and approved by the central reader to perform [REDACTED], full-field visual evoked potential, and [REDACTED].

[REDACTED]

¹² Adverse event/serious adverse event monitoring will be recorded after informed consent form sign-off through the end-of-study visit.

CONFIDENTIAL

The information contained herein may not be used, disclosed, or published without the written consent of Biogen MA Inc.

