5.3. Overview of Multiple Sclerosis

MS is a chronic disabling neurological disease that affects an estimated 1 million people in North America and Western Europe. It is a disease of young adults, primarily women, with disease onset typically occurring between the ages of 20 and 40 years [Weinshenker 1989]. It is the most frequent cause of nontraumatic neurological disability affecting young adults in the Western world. Although the etiology is uncertain, evidence suggests that MS is, in part, an autoimmune disease directed against protein components of myelin. The diagnosis of clinically definite multiple sclerosis (CDMS) has traditionally been made on the basis of clinical criteria and requires that a patient experience at least 2 neurologic events consistent with demyelination, separated both in time and in location in the CNS [Poser 1983]. More recent diagnostic criteria have allowed for less than 2 neurologic attacks, when there is supportive laboratory evidence based on magnetic resonance imaging (MRI) or cerebrospinal fluid (CSF) results [McDonald 2001]. The majority of patients with MS start out with a clinical course characterized by episodes or attacks (relapses) of neurologic dysfunction, which occur over many years. This phase of the disease is called relapsing-remitting multiple sclerosis (RRMS). Symptoms of such relapses include loss of vision or double vision, numbness or tingling sensation in the extremities, muscle weakness, slurred speech, difficulty with coordination, and bladder dysfunction. Patients having the first clinical attack are referred to as clinically isolated syndrome (CIS). The most common CIS types are AON, transverse myelitis, and brainstem attack. Patients with CIS with characteristic brain MRI lesions are considered to be having MS by the most recent diagnostic McDonald criteria [Polman 2011]. Patients with CIS without brain lesions are at low risk of developing MS. Early in the course of relapsing MS, the signs and symptoms tend to subside completely after each attack. Over time, there tends to be incomplete recovery from such attacks. The majority of patients with relapsing MS accumulate some

CONFIDENTIAL

The information contained herein may not be used, disclosed, or published without the written consent of
Biogen MA Inc.

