14.1. Efficacy

14.1.1. Analysis Population

Analysis of efficacy endpoints will be based on all enrolled subjects who complete the 1-day assessments.

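### The lead Kaplan-Meier analysis of CDMS uses a per-protocol set defined by events after its time origin; the ITT analysis, planned only as sensitivity, should lead

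*SAP*

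**What the plan says.** SAP 3.3.3 counts subjects with CDMS by arm and states that "the time to diagnosis of CDMS in 215ON203 from the diagnosis of AON in 215ON201 will be analyzed by the Kaplan-Meier" product-limit estimate, with the 10th, 25th and 50th percentiles by treatment group. The clock starts at the diagnosis of AON, and subjects without the event are censored at last study contact.

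SAP 3.3.3 sets no population of its own for CDMS, so the general rule in SAP 3.3.1 applies: "The analyses performed in the per-protocol population will be considered the primary analyses", with ITT as sensitivity.

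SAP 3.1 defines per-protocol as ITT subjects "who completed the 215ON201 study, did not miss more than one dose of BIIB033 or placebo", and who "did not receive MS modifying therapies during study 215ON201". ITT itself needs at least one dose in 215ON201 and subjects who "completed at least one of the 1-day assessments in this study".

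Protocol 14.1.1 has no per-protocol restriction: "Analysis of efficacy endpoints will be based on all enrolled subjects who complete the 1-day assessments".

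**The concern.** A time-to-event curve should start from a group that can be identified at its time origin. Here that origin is AON diagnosis, and each per-protocol condition is decided later, during 215ON201. The therapy condition is the most serious, because starting an MS-modifying drug is a natural consequence of converting. A subject who converts and is treated in the parent study leaves both numerator and denominator of the lead curve, and this may happen at different rates in the two arms.

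The effect need not be downward. The exclusion is on therapy, not on CDMS, and Protocol 5.3 notes: "Patients with CIS with characteristic brain MRI lesions are considered to be having MS by the most recent diagnostic McDonald criteria". Subjects treated on that basis without having reached CDMS would be dropped as well, which pushes the estimate the other way.

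CDMS is the first secondary endpoint listed in Protocol 6.2. The visible SAP text for it plans only counts, descriptive statistics and Kaplan-Meier estimates, so the lead table is the result that readers will take away. They could not tell from it whether incidence and the early percentiles are too low, right or too high.

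**Working it through.** The documents state no CDMS rate, event count or hazard ratio, so there is no figure to reproduce. The calculation below is an illustration.

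**From the documents.** Last parent-study visit at Week 32; follow-up visit 2 years later, up to 12 months more; 41 subjects dosed per arm. Horizon: 32 + 104 = 136 weeks, or 136 + 52 = 188 weeks at the limit.

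**Assumed.** Constant hazard; true incidence F of 20% to 50% at the horizon; clock taken from first dose, because the interval from AON diagnosis to first dose is not given. Let q1 be the share of subjects converting in the first 32 weeks who are dropped from per-protocol, and q0 the share of everyone else dropped.

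**Formulas.** λ = −ln(1 − F)/136 and F32 = 1 − exp(−32λ). Per-protocol incidence at the horizon is

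PP = [(1 − q1)·F32 + (1 − q0)·(F − F32)] / [(1 − q1)·F32 + (1 − q0)·(1 − F32)].

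PP equals F when q1 = q0, falls below F when q1 > q0 and rises above it when q1 < q0.

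**At F = 40%.** λ = 0.5108/136 = 0.00376 per week; F32 = 0.113; F − F32 = 0.287; 1 − F32 = 0.887.

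| q1 | q0 | PP incidence | Error (points) |
|---|---|---|---|
| 0.50 | 0 | 0.3434/0.9434 = 36.4% | −3.6 |
| 0.80 | 0.30 | 34.7% | −5.3 |
| 0.50 | 0.30 | 38.0% | −2.0 |
| 0.50 | 0.50 | 40.0% | 0 |
| 0.25 | 0.30 | 40.5% | +0.5 |
| 0.25 | 0.50 | 0.2283/0.5283 = 43.2% | +3.2 |

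**Range when only early converters are dropped (q0 = 0).** Smallest: F = 20%, q1 = 0.25, F32 = 0.051, PP = 19.0%, an error of −1.0 point. Largest: F = 50%, q1 = 1, F32 = 0.150, PP = 41.1%, an error of −8.9 points. If the same incidence is reached only at 188 weeks, the range is −0.75 to −6.3 points.

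**10th percentile at F = 40%.** True value: −ln(0.9)/λ = 28.1 weeks. With (q1, q0) = (0.5, 0), solve F(t) = 0.10 × 0.9434 + 0.5 × 0.113 = 0.151, giving 43.6 weeks. With (0.25, 0.5) the percentile falls before Week 32: F(t) = 0.10 × 0.5283/0.75 = 0.0704, giving 19.4 weeks.

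**Between arms.** With no true effect, F = 40%, q0 = 0, and half of early converters dropped in one arm but none in the other, the arms read 36.4% and 40.0%, a false difference of 3.6 points.

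**Scale.** With all 41 subjects per arm, the standard error at 40% is √(0.4 × 0.6/41) = 7.7 points, and 7.7 × √2 ≈ 10.8 points for a difference. Every error above is smaller than the latter.

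**The case against.** The strongest reply is that the label matters little. SAP 3.3.1 already requires both populations, so an ITT table by arm will exist. SAP 3.3.3 names no test for CDMS, and no visible decision depends on which table leads. Nor is any bias demonstrated: every rate above is assumed, the results run from −8.9 through zero to +3.2 points, and even the extreme is below the standard error of an arm difference. This stands as a limit on weight. It does not justify leading with an estimate whose error cannot be signed when a table without that exclusion is already planned.

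Second, ITT also selects on a later event, attendance at 215ON203 two or more years after time zero, and loss to return could be the larger selection. That is correct. ITT removes the completion, dosing and therapy conditions but not attendance, which has to be disclosed. ITT also does not match Protocol 14.1.1 exactly: the protocol asks for the assessments to be completed, the SAP for at least one. It is only closer.

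Third, per-protocol is the parent-study set carried forward, so it was not chosen on 215ON203 results. That is fair, but the therapy condition still falls after time zero and can be caused by the event. For completion and missed doses no link to CDMS is shown; they share only the timing problem.

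**Conclusion.** The concern holds. As written, the lead CDMS curve is restricted by conditions settled after its time origin, one of them plausibly a result of the event, and the restriction is absent from Protocol 14.1.1. Its size cannot be derived from the documents. Under the stated assumptions, incidence is understated by 1.0 to 8.9 points if only early converters are dropped; the error vanishes or reverses if enough other subjects are dropped too. The matter affects how a descriptive secondary endpoint is read, not a controlled error rate or a detectable treatment effect. It should be changed because the better analysis is already planned.

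A separate wording point: SAP 3.3.3 moves between CDMS, confirmed MS and MS without defining confirmed MS. Since Protocol 5.3 distinguishes CDMS from MS by the McDonald criteria, the event needs one definition.

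**What to change.** In SAP 3.3.3:

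- Make ITT by randomised arm the primary analysis for CDMS incidence and time to CDMS, as a stated exception to SAP 3.3.1.
- Count CDMS diagnosed during 215ON201 and name parent-study records as the source. The 215ON203 history alone would miss these cases: "Medical history will be taken from after last study visit in Study 215ON201" (Protocol 4.2, footnote 3).
- Show per-protocol as supportive only, either with its clock started at parent Week 32 among subjects event-free then, or with the number of CDMS cases it excludes in each arm.
- Use CDMS as the single event; define confirmed MS or report it separately.
- State that ITT still conditions on attending 215ON203, and report by arm how many of the 82 dosed subjects did not attend. If parent-study dates allow, add a sensitivity curve from all 82, with non-attenders who have no recorded CDMS censored at last contact.

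The cost is SAP wording, since the ITT run is already planned, plus retrieval of CDMS dates from 215ON201. The documents do not confirm that the parent study recorded those dates in usable form, so this should be checked first.
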